6.2.1.3 Assessment plausibility of the proportional hazards assumption

If the hypothesis of non-inferiority is accepted the plausibility of the proportional hazards assumption will be assessed by visually comparing the plot of the log of cumulative hazard , in the ITT data scope, between treatments. The following SAS code may be used:

```
proc phreg data=work.infile (where=(treat=1));
model d2fDTE*DTE(0)=treat;
baseline out=work.ch_t1 cumhaz=ch;
run;
proc phreg data=work.infile (where=(treat=0));
model d2fDTE*DTE(0)=treat;
baseline out=work.ch_t0 cumhaz=ch;
run;
data work.log_ch;
set work.ch_t1
      work.ch_t0;
if ch ne 0 then log_ch=log(ch);
run;

proc sgrender data=work.log_ch template=comp_log_CH;
dynamic xvar="d2fDTE" yvar="log_ch" groupvar="treat";
run;

/*
where

```

```
work.infile = name of source dataset
treat       = randomization code
DTE         = death and thromboembolic event
d2fDTE     = days to first DTE (since randomization)
comp_log_ch = proc template for a log of cumulativehazards plot
*/

```

By additionally adding a time-varying covariate, an interaction between the predictor and the time the plausibility of proportional hazards is assessed, the following SAS code may be used:

```
proc phreg data= work.infile;
model d2fDTE * DTE (0)=treat treat_time;
treat_time = treat*log(d2fDTE);
proportionality_test: test treat_time;
run;
/*
where
work.infile = name of source dataset
treat       = randomization code
DTE         = death and thromboembolic event
d2fDTE     = days to first DTE (since randomization)
*/

```

6.3 Pharmacokinetics / pharmacodynamics

Not applicable.

6.4 Safety

The primary safety endpoint

The primary safety endpoint is primary bleeding event (PBE), defined as the composite of life-threatening, disabling or major bleeds classified according to the VARC definitions following the BARC classification. This is: Life-threatening or disabling bleeds; BARC type 3b, 3c or 5 and for Major bleeds; BARC type 3a.

The secondary safety endpoints

The secondary safety endpoints are bleeding complications according to:

- The composite of TIMI major or minor bleeds
- ISTH major bleeding
- The composite of BARC 2, 3 or 5 bleeds

Investigator reported events

- Serious adverse events (SAEs)

- Adverse events of special interest
 - Pericardial bleedings
 - Pulmonary alveolar bleedings/pulmonary bleeding
- Non-serious Adverse Events

6.4.1 Analysis of the safety endpoints

6.4.1.1 Analysis of the primary safety endpoint

The descriptive analysis of the primary safety endpoint (PBE) and the secondary safety endpoints are performed on the FAS under the ITT scope

Kaplan-Meier curves, one-sided log rank p-value, number of patients with event and incidence rate are provided to evaluate the timing of event occurrence in the different treatment groups and the consistency of the respective treatment effects for all time points.. This is done analogue to the primary efficacy endpoint as described in section [6.2.1.2](#)

If the assumption of proportional hazards is plausible (see section [6.2.1.3](#)), Hazard ratio and corresponding two-sided 95% confidence intervals are estimated.. This is done analogue to the primary efficacy endpoint as described in section [6.2.1.2](#).

The analysis of the primary safety endpoint is visualized in [flowchart 3](#) in appendix I.

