	
• Severe renal impairment (eGFR < 30 mL/min/1.73 m²) or on dialysis, or post-TAVR unresolved acute kidney injury with renal dysfunction stage 2 or higher• Moderate and severe hepatic impairment (Child-Pugh Class B or C) or any hepatic disease associated with coagulopathy. 
Screening, IC and randomization:
 
Subjects are screened for inclusion after TAVR. Consenting subjects must be randomized within 1-7 days after a successful TAVR and before hospital discharge.

Study design	Event-driven, randomized, open-label with blinded endpoint evaluation, parallel-group, active-controlled, multicenter, international study
Methodology	
The primary comparison will be to test the superiority of a rivaroxaban-based strategy to an antiplatelet-based strategy with respect to the primary efficacy endpoint. This comparison is preceded by a non-inferiority test that must be satisfied.
 
Estimates of the hazard ratio for bleeding events together with their 95% confidence intervals will be calculated for descriptive purposes.

Type of control	Control treatment strategy is composed of active treatments and is in line with the current standard of care.
Clinical Event Committee	Yes
Data Safety Monitoring Board	Yes
Number of subjects	A total of 1520 subjects will be randomized.
Primary variable(s)	
Primary Efficacy Endpoint: death or first adjudicated thromboembolic event (DTE) defined as the composite of all-cause death and adjudicated any stroke, myocardial infarction (MI), symptomatic valve thrombosis, pulmonary embolism (PE), deep vein thrombosis (DVT), or non-CNS systemic embolism.
 
Primary Safety Endpoint: primary bleeding event (PBE) defined as the composite of adjudicated life-threatening, disabling or major bleeding, classified according to the valve academic research consortium (VARC) definitions following the bleeding academic research consortium (BARC) classification.

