10.3.7. Analysis of the safety variables

This section was modified with Amendment 3. For details, see Section 15.2.

The analysis of the primary safety variable is performed on the Full Analysis Set (FAS) under the ITT data scope — that is, events are analyzed irrespective of their time of occurrence relative to termination of assigned study treatment strategy. Follow-up is censored at the last date of known outcome status or at the efficacy cut-off date, whichever comes first.

Kaplan-Meier estimates of cumulative risk and cumulative hazard functions for the primary safety variable are provided to evaluate the timing of event occurrence in the different treatment groups and the consistency of the respective treatment effects for all time points.

If the proportional hazards assumption holds for the primary safety variable, hazard ratio and corresponding two-sided 95% confidence intervals are estimated based on a Cox proportional hazards models.

On treatment analyses, pre-NOAF and post-NOAF analyses of the primary safety variable are performed as exploratory analyses.

All of the above analyses of the primary safety variable are descriptive, without formal statistical tests being performed.

The analyses of secondary safety variables are similar to those for secondary efficacy variables, without any sequential order.

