6.2.1.2 Testing for superiority

If, for the primary efficacy endpoint (DTE), non-inferiority of the rivaroxaban-based strategy can be claimed, superiority of the rivaroxaban-based strategy for the primary efficacy endpoint (DTE) is tested with the following hypothesis (H_0) at the significance level of 2.5%

$H_0: S_{RIV}(t) = S_{APT}(t)$ for all time points $t \geq 0$, (i.e. “there is no difference between the rivaroxaban-based treatment group and the antiplatelet-based control group regarding the primary efficacy endpoint at all time points”)

The one-sided alternative hypothesis (H_1) is:

$H_1: S_{RIV}(t) > S_{APT}(t)$ for at least one time point $t \geq 0$, and $S_{RIV}(t) \geq S_{APT}(t)$ for all time points ≥ 0 (i.e. “there is difference between the two groups in favor of the rivaroxaban-based treatment group for the primary efficacy endpoint at all time points”)

where S_{RIV} denotes the event-free survival function of the rivaroxaban-based treatment group and S_{APT} denotes the event-free survival function of the antiplatelet-based treatment group.

The following decision rule to test the null hypothesis is applied:

According to the size of this study, it is justified to assume under H_0 a sufficiently close approximation of the one-sided log-rank test to the normal distribution. If the z value from the one-sided log-rank test (for the difference $S_{RIV}(t) - S_{APT}(t)$) is larger than the critical quantile from the normal distribution ($z_{0.975} = 1.96$), the null hypothesis is rejected in favor of the alternative hypothesis.

Kaplan-Meier curves, one-sided log rank p-value, number of patients with event and incidence rate are provided to evaluate the timing of event occurrence in the different treatment groups and the consistency of the respective treatment effects for all time points.

The following SAS code may be used:

```
proc lifetest data=work.infile  notable;
  time d2fDTE*DTE(0);
  strata treat /test=(logrank);
run;
/*
where
work.infile = name of source dataset
treat       = randomization code
DTE         = death and thromboembolic event
d2fDTE     = days to first DTE (since randomization)
*/

```

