If, for the primary efficacy endpoint (DTE), non-inferiority of the rivaroxaban-based strategy can be claimed and the assumption of proportional hazards is plausible (see section 6.2.1.3), Hazard ratio and corresponding two-sided 95% confidence intervals are estimated. This is based on a Cox proportional hazards model, and will be reported descriptively. The parameter estimate β ($=\ln(HR)$), its standard error, p-value, and 95% Confidence Limits are calculated according to the maximum partial likelihood method (ML), with Breslow's approximation for ties (phreg).

The following SAS code may be used:

```
proc phreg data=work.infile ;
  model d2fDTE*DTE(0)=treat /risklimits ;
run;
/*
where
work.infile = name of source dataset
treat       = randomization code
DTE         = death and thromboembolic event
d2fDTE     = days to first DTE (since randomization)
*/

```

If superiority of DTE can be declared for the rivaroxaban-based strategy the secondary efficacy and net-benefit variables are tested for superiority sequentially in a hierarchical order, first the composite of cardiovascular death, any stroke, myocardial infarction, symptomatic valve thrombosis, pulmonary embolism, deep vein thrombosis, or non-CNS systemic embolism, second the net-clinical-benefit defined as the adjudicated composite of all-cause death, any stroke, myocardial infarction, symptomatic valve thrombosis, pulmonary embolism, deep vein thrombosis, non-CNS systemic embolism (efficacy); life-threatening, disabling and major bleeds (safety).

The superiority analysis are carried out under the ITT data scope.

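### SAP 6.4.1.1 adds a one-sided log-rank p-value for primary bleeding events that borrows the efficacy direction, so excess bleeding on rivaroxaban would print as a p-value near 1

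*SAP*

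**What the plan says.** **Protocol 10.3.7** lists three outputs for the primary safety variable: Kaplan-Meier estimates, cumulative hazards and a conditional Cox estimate, "If the proportional hazards assumption holds for the primary safety variable, hazard ratio and corresponding two-sided 95% confidence intervals are estimated". It then says: "All of the above analyses of the primary safety variable are descriptive, without formal statistical tests being performed". No p-value is listed.

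**Protocol synopsis (Methodology)** has no such condition: "Estimates of the hazard ratio for bleeding events together with their 95% confidence intervals will be calculated for descriptive purposes".

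**SAP 6.4.1.1** also calls the PBE analysis descriptive, but its outputs are "Kaplan-Meier curves, one-sided log rank p-value, number of patients with event and incidence rate are provided to evaluate the timing" of events. It adds "This is done analogue to the primary efficacy endpoint as described in section" 6.2.1.2. It gives no hypothesis, significance level or decision rule for bleeding, and keeps the proportional-hazards condition on the hazard ratio.

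**SAP 6.2.1.2** is the efficacy superiority test. Its alternative is that "there is difference between the two groups in favor of the rivaroxaban-based treatment group for the primary efficacy endpoint at all time points". Its statistic is the log-rank z for survival on rivaroxaban minus survival on antiplatelet therapy, and it rejects when z exceeds 1.96.

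**SAP section 7**, where changes in the planned analysis would be declared, records none.

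**The concern.** PBE is a harm endpoint, and the result the safety table most needs to show clearly is more bleeding on rivaroxaban. A one-sided p-value built to detect benefit moves the wrong way: the stronger the evidence of excess bleeding, the closer it gets to 1. A reader who sees 0.99 beside the bleeding curves could take it as reassurance when the same data give a two-sided p below 0.01.

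The protocol did not plan this number, and the SAP does not declare it as an addition. The output sentence in 6.4.1.1 closely repeats the one in 6.2.1.2, which suggests that efficacy wording was carried over to safety without reconsidering the direction.

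**Working it through.** **Step 1. Direction, from the text.** SAP 6.4.1.1 refers to 6.2.1.2. There z is positive when rivaroxaban has the better event-free survival, and the rejection region is the upper tail. The matching one-sided p-value is 1 − Φ(z). More bleeding on rivaroxaban makes z negative and p greater than 0.5. The suggested code ("strata treat /test=(logrank") sets no side, so the direction comes from the text of 6.2.1.2 alone.

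**Step 2. Check of the approximation.** The current text gives no event count, margin or power for bleeding, so there is no bleeding figure to reproduce. The efficacy design in Protocol 10.4 can be reproduced with the same formula:
- HR = ln(1 − 0.264)/ln(1 − 0.33) = 0.7654, as stated.
- With 440 events, power = Φ(|ln 0.7654| × √440/2 − 1.96) = Φ(2.804 − 1.96) = 0.80, as stated.

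**Step 3. An illustrative bleeding count (assumptions).**
- The Protocol Introduction puts late major bleeding at about 6% between 30 days and 1 year (335 days). At constant hazard, the 540-day risk is 1 − 0.94^(540/335) = 9.5%.
- Assume 15% non-bleeding death by day 540 in both arms, 760 subjects per arm and a true HR of 1.5.
- Over 540 days the cumulative hazards are 0.0997 for bleeding (control), 0.1496 for bleeding (rivaroxaban) and 0.1625 for death.
- Control: 0.0997/0.2623 × (1 − e^−0.2623) = 8.77%. Rivaroxaban: 0.1496/0.3121 × (1 − e^−0.3121) = 12.85%.
- Events: 760 × (0.0877 + 0.1285) = 164. With 10% deaths instead, 169.

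**Step 4. The p-value that would print.** With D events and 1:1 allocation, z = −ln(1.5) × √D/2, and the 95% CI is 1.5 × exp(±1.96 × 2/√D). The 80, 100 and 200 events are assumed, to show a range.

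| Events (assumed HR 1.5) | z | 95% CI | One-sided p, direction of 6.2.1.2 | One-sided p, harm direction | Two-sided p |
|---|---|---|---|---|---|
| 80 | −1.81 | 0.97–2.33 | 0.965 | 0.035 | 0.070 |
| 100 | −2.03 | 1.01–2.22 | 0.979 | 0.021 | 0.043 |
| 164 | −2.60 | 1.10–2.04 | 0.995 | 0.005 | 0.009 |
| 200 | −2.87 | 1.14–1.98 | 0.998 | 0.002 | 0.004 |

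The pattern does not depend on HR 1.5. At 160 events, HR 1.2 gives 0.876 (two-sided 0.249), and HR 2.0 gives a value that rounds to 1.000.

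**Step 5. The synopsis and the body.** The synopsis promises the bleeding HR and CI outright. Protocol 10.3.7 and SAP 6.4.1.1 give them only if proportional hazards is accepted. If it is not, the synopsis output is missing and the one-sided log-rank p-value is the only p-value listed for PBE in 6.4.1.1.

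**The case against.** The other side has a good deal to say, and most of it limits the size of the point.

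- **The analysis is labelled descriptive.** This stands. A reader might infer that the SAP has turned bleeding into a confirmatory test. It has not: no hypothesis, alpha or decision rule is attached to PBE. Protocol 10.1 also leaves analytic detail and output tables to the SAP. But a descriptive number still has to be readable, and the protocol's list for PBE contains no p-value.
- **A direction is given.** This stands. A reader might infer that the direction is simply unstated. The cross-reference to 6.2.1.2 supplies both the statistic and the tail. The fault is that the borrowed direction is a benefit direction, unsuited to a harm endpoint.
- **The harm would not be hidden.** This also stands. Counts, incidence rates and Kaplan-Meier curves are unconditional. If proportional hazards is accepted, the HR with its two-sided CI is reported too, and the Cox output of 6.2.1.2 ("its standard error, p-value, and 95% Confidence Limits are calculated according to the maximum partial likelihood method") comes with it. The one-sided value also converts to the two-sided one once its direction is known.
- **The conditional HR is not a SAP error.** Correct: Protocol 10.3.7 has the same condition, so the inconsistency is between the synopsis and the two detailed sections.
- **Secondary safety.** A reader might infer that one-sided secondary safety analyses are also a deviation. The documents do not support that: Protocol 10.3.7 itself makes them similar to the secondary efficacy analyses, and SAP 6.4.1.2 follows it.
- **Section 7 is thin evidence.** Its heading also covers document history, and figures near the entry are not shown. Flowchart 3, which depicts this analysis, is not visible either and may say more.

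**Conclusion.** The point holds, at minor severity. SAP 6.4.1.1 adds a p-value that Protocol 10.3.7 does not list, and by its own cross-reference the value points towards benefit. At an assumed HR of 1.5 it would print as 0.979 with 100 events and 0.995 with 164, against two-sided values of 0.043 and 0.009. The HR, bleeding rate, death rate and event counts are illustrative assumptions. The direction of the effect is not: it follows from the test statistic and tail that the SAP names. The reading of the text is subject to flowchart 3, which could not be checked. The consequence is confined to one misleading entry in the primary safety output. The efficacy conclusion, type I error, sample size and power are unchanged.

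**What to change.** 1. In SAP 6.4.1.1, delete the one-sided log-rank p-value for PBE, or replace it with a two-sided nominal p-value labelled descriptive. Check that flowchart 3 agrees.
2. Record the change in SAP section 7.
3. Reconcile the synopsis with Protocol 10.3.7 and SAP 6.4.1.1 on the bleeding HR, preferably by reporting the HR and two-sided 95% CI whatever the proportional-hazards check shows.

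The cost is a few words in the SAP and a matching clarification in the protocol. No new data are needed, and the suggested code can stay. It is best settled before results by treatment group are seen, so that the presentation of bleeding cannot appear to have been chosen afterwards.

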6.4.1.2 Analysis of the secondary safety endpoints

The secondary safety endpoints are descriptively analyzed similar to those for secondary efficacy variables, without any sequential order.

The analysis of the secondary safety endpoints are visualized in [flowchart 2](#) in appendix I.

6.4.1.3 Analysis of the investigator reported endpoints

SAEs are descriptively reported (frequencies of events and frequencies of patients with any event) by MedDRA SOC and PT.

Adverse events of special interest (pericardial bleedings and pulmonary alveolar bleedings/pulmonary bleedings) are descriptively reported (frequencies of events and frequencies of patients with any event)

Non-serious AEs, are descriptively reported (frequencies only) by MedDRA SOC, outcome of event, reasonable causal relationship to ASA, -clopidogrel, -rivaroxaban and -VKA, and Action taken with ASA, - clopidogrel, -rivaroxaban and -VKA.

6.5 Other analysis

Pre-NOAF and post-NOAF analysis are carried out as an exploratory analysis for the primary efficacy variable (DTE). On treatment, pre-NOAF and post-NOAF analysis are carried out as an exploratory analysis for the primary safety (PBE) variable. The analyses are done analogue to the superiority HR analysis as described in [6.2.1.2](#) and are visualized in [flowchart 4](#).

The separate components of the adjudicated primary efficacy and safety endpoint are analyzed exploratory and analogue to the superiority HR analysis as described in [6.2.1.2](#). The separate components of the adjudicated primary efficacy and safety endpoint are:,

- All-cause death
- Any stroke
- Myocardial infarction
- Symptomatic valve thrombosis
- Pulmonary embolism
- Deep vein thrombosis
- Non-CNS systemic embolism
- Life-threatening or disabling bleeds (BARC type 3b, 3c or 5)
- Major bleeds (BARC type 3a).

The following details of NOAF are summarized by treatment:

- Subjects with NOAF reported on ECG but without medication switch
- Subjects with medication switch but without ECG evidence of NOAF
- Subjects with both ECG evidence and medication switch

Medication switch here means: requiring treatment with high dose oral anticoagulation as specified in 3.2.

Mean transaortic valve pressure gradient is measured by echocardiogram (TTE or TEE) at screening and at approximately 360 days after randomization. The difference between 360 days and screening is derived and analyzed exploratory by using a t-test.

The analysis the other variables are visualized in [flowchart 2](#) in appendix I.

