5.3.3. Other variable(s)

This section was modified with Amendment 3. For details, see Section [15.2](#).

The individual components of the primary efficacy and safety endpoint will be assessed as other endpoints.

The mean transaortic valve pressure gradient at approximately 360 days after randomization as measured by routine echocardiogram (TTE or TEE), if available, will be captured in the eCRF and it is considered as an exploratory study endpoint.

End of study

The end of the study as a whole will be reached as soon as the last visit of the last subject has been reached in all centers in all participating countries.

The primary completion event for this study occurs when the 440th subject experiences a positively adjudicated primary efficacy endpoint or earlier if the event rate is unexpectedly low. The efficacy cut-off date is defined as the date of the primary completion event.

For practical purposes, the anticipated efficacy cut-off date is set based on a projection of the date of the primary completion event before 400 subjects have experienced a positively adjudicated primary efficacy endpoint. When the anticipated efficacy cut-off date is set, on-site visit will be scheduled for all subjects within 6 weeks.

The primary completion date for this study according to the FDA Amendment Act is specified in a separate document (not part of this study protocol).

6. Study population

This section was modified with Amendment 3. For details, see Section 15.2.

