6.1. Inclusion criteria

Potential subjects must satisfy the following criteria to be enrolled in the study:

- Man or woman of 18 years of age or older
- Have a successful TAVR of an aortic valve stenosis (either native or valve-in-valve)
- Via iliofemoral or subclavian access
- With any approved/marketed TAVR device
- Provide written IC

Successful TAVR (29) is defined:

1. Correct positioning of a single prosthetic heart valve into the proper anatomical location.
2. Intended performance of the prosthetic heart valve - presence of all 3 conditions post-TAVR:
 - a. mean aortic valve gradient < 20 mmHg
 - b. peak transvalvular velocity (aortic valve maximum velocity) < 3.0 m/s
 - c. no severe or moderate aortic valve regurgitation
3. Absence of periprocedural complications, such as:
 - a. Any type of periprocedural stroke
 - b. VARC graded life-threatening bleeding
 - c. Acute coronary artery obstruction requiring intervention

- d. Major vascular complication requiring intervention (including access-site vascular complications, any new ipsilateral peripheral ischemia, distal embolization from a vascular source, aortic dissection, aortic rupture, ventricular perforation, cardiac tamponade, and annulus rupture)
- e. Unresolved acute valve thrombosis
- f. Any requirement of a repeat procedure

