- Demographic data check
- Medical history
- Prior medication
- TAVR assessment
- Laboratory assessments (see Section [9.6.3.1](#))
- Routine echocardiogram (TTE or TEE) post-TAVR and before hospital discharge if available per local standard of care for TAVR.

Visit 1 – Baseline / Randomization

- Reconfirmation of eligibility (in- and exclusion criteria)
NB: No subject may be randomized unless adherence to all selection criteria as given in section [6](#) is established.
- Concomitant medication check
- Physical examination
- Vital signs
- 12-lead electrocardiogram (ECG) or any other method documenting heart rhythm (e.g. ECG strip) able to exclude atrial fibrillation
- Randomization via IxRS (see Section [7.3](#))

The following procedures will be performed 1-7 days after the index-TAVR, **after randomization and before discharge**:

- First administration of assigned treatment strategy, including instructions on the use of study's treatment strategies
- Continuous assessment of (S)AEs
- Assess if any efficacy and/or safety endpoints occurred
- Assess if NOAF occurred

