The following procedures will be performed during this telephone contact:

- Concomitant medication check
- Continuous assessment of (S)AEs
- Assess if any efficacy and/or safety endpoints occurred
- Assess if NOAF has been diagnosed

Visit 5 - On-site visit: 360 days (\pm 30 days)

The following procedures will be performed during this on-site visit:

- Concomitant medication check
- Physical examination
- Vital signs check
- 12-lead electrocardiogram (ECG)
- Continuous assessment of (S)AEs
- Assess if any efficacy and/or safety endpoints occurred
- Assess if NOAF occurred
- Prescription of assigned therapy and rivaroxaban dispensation, as needed
- Routine echocardiogram (TTE or TEE) approximately at 360 days after randomization if available per local standard of care for TAVR.

NB: An echocardiogram at 360 ± 30 days after randomization is preferred. However, if unavailable last available echocardiogram between 180-360 days after randomization can be considered.

Visit 6 – On-site visit: 540 days (\pm 30 days)

The following procedures will be performed during this on-site visit:

- Concomitant medication check

- Physical examination
- Vital signs check
- 12-lead electrocardiogram (ECG)
- Continuous assessment of (S)AEs
- Assess if any efficacy and/or safety endpoints occurred
- Assess if NOAF occurred

Visit 7 through Visit n - On-site visit: 720 days and every 180 days (\pm 30 days)

The following procedures will be performed during this on-site visit:

- Concomitant medication check
- Physical examination
- Vital signs check
- 12-lead electrocardiogram (ECG)
- Continuous assessment of (S)AEs
- Assess if any efficacy and/or safety endpoints occurred
- Assess if NOAF occurred

Unscheduled on-site visit - NOAF-related

In the event of NOAF after randomization, the assigned therapy should be modified as defined per protocol (Section 7.1) and the following procedures should be performed during the unscheduled on-site visit:

- Concomitant medication check
- Physical examination
- Vital signs check
- 12-lead electrocardiogram (ECG)
- Continuous assessment of (S)AEs
- Assess if any efficacy and/or safety endpoints occurred
- For subjects in the rivaroxaban-based strategy:
 - Assess creatinine clearance
 - Dispense dose of rivaroxaban according to 7.1.1.1
- For subjects in the antiplatelet-based strategy:
 - Subjects will be transitioned to an open-label vitamin K antagonist (VKA) strategy according to 7.1.2.1 and to the appropriate local guidelines

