9.7. Other procedures and variables

Echocardiography

Findings from routine echocardiograms (either TTE or TEE) will be collected post-TAVR and at approximately 360 days after randomization (360 ± 90 days or last available between 180-360 days) if available according to the local standard of care for TAVR. Selected hemodynamic parameters will be recorded in the eCRF. Copies of recorded echocardiograms are stored in the patient hospital files.

If an investigational study center is routinely collecting 3D TEE in their post-TAVR subjects, these recordings may be used as the scheduled echocardiograms described above, as long as the sponsor/designated CRO is informed and has approved it accordingly.

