2.3 Other Objectives

Other secondary efficacy and safety objectives are to compare the effects of a rivaroxaban-based strategy and an antiplatelet-based strategy with respect to the individual components of the composite of DTE and of the composite of life threatening, disabling, or major bleeding, respectively.

The effect of rivaroxaban-based strategy, following successful TAVR, compared to an antiplatelet-based strategy, on the mean transaortic valve pressure gradient at 360 days as measured by echocardiography will be assessed as an exploratory study endpoint.

3. Study Design

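### The t-test on change in transaortic gradient is valid but usually less precise than adjusting for the recorded screening gradient; the SAP also sets no analysis window for the day-360 echo

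*SAP*

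**What the plan says.** SAP 2.3 sets out to compare the strategies "on the mean transaortic valve pressure gradient at 360 days as measured by echocardiography will be assessed as an exploratory study endpoint". Protocol 5.3.3 defines the variable as a level, not a change: "The mean transaortic valve pressure gradient at approximately 360 days after randomization as measured by routine echocardiogram (TTE or TEE), if available".

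SAP 6.5 takes the gradient "at screening and at approximately 360 days after randomization" and then says: "The difference between 360 days and screening is derived and analyzed exploratory by using a t-test". It names no covariate and no numeric window. It does not say that the t-test is two-sample; that is inferred from the between-strategy objective.

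The baseline value comes from a routine post-procedure echo. Protocol 9.2.1 lists "Routine echocardiogram (TTE or TEE) post-TAVR and before hospital discharge if available per local standard of care for TAVR". Eligibility (Protocol 6.1) requires "mean aortic valve gradient < 20 mmHg" after the procedure.

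On the timing of the later echo, Protocol 9.2.2 (Visit 5) says "An echocardiogram at 360 ± 30 days after randomization is preferred", with the last echo between days 180 and 360 as a fallback. Footnote h to the schedule in Protocol 9.1 says the same. Protocol 9.7 gives "360 ± 90 days or last available between 180-360 days".

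**The concern.** The trial records the screening gradient wherever a routine echo exists, yet the plan only subtracts it. Subtraction forces the baseline coefficient to be exactly 1. A regression estimates that coefficient from the data and so uses the baseline at least as well.

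Echoes are collected only where local practice provides them, and neither Protocol 11.4 nor SAP 4.3 imputes missing continuous values. The analysis will therefore rest on fewer pairs than subjects randomized, and precision given away cannot readily be recovered.

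The timing rule is a separate and smaller matter. The protocol gives two tolerances and the SAP chooses neither, so the programmer has no fixed rule for which echo enters the analysis. In an open-label trial that rule is better settled in advance.

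**Working it through.** **The plan's own figure.** The documents state no sample size, power, SD or target difference for this endpoint, so there is nothing to reproduce.

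**Inputs.** Let r be the baseline SD divided by the follow-up SD, and rho the correlation between the two gradients. Neither is in the documents. The assumed ranges are r from 0.5 to 1.0 and rho from 0.3 to 0.7.

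**Formulae** (large samples, in units of the follow-up variance):

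- Change score: Var = 1 + r² − 2·rho·r
- Adjusted model: Var = 1 − rho²
- Difference: (1 + r² − 2·rho·r) − (1 − rho²) = (r − rho)²

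The difference is a square, so the adjusted model is never less precise. The two are equal exactly when rho = r. With r = 1, the ratio of adjusted to change-score variance reduces to (1 + rho)/2.

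**Results.** Extra pairs needed by the t-test = Var(change)/Var(adjusted) − 1.

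| r | rho | Var(change) | Var(adjusted) | Extra pairs | Narrowing of CI with adjustment |
|---|---|---|---|---|---|
| 1.0 | 0.3 | 1.400 | 0.91 | 54% | 19.4% |
| 1.0 | 0.5 | 1.000 | 0.75 | 33% | 13.4% |
| 1.0 | 0.7 | 0.600 | 0.51 | 18% | 7.8% |
| 0.75 | 0.3 | 1.1125 | 0.91 | 22% | 9.6% |
| 0.75 | 0.5 | 0.8125 | 0.75 | 8% | 3.9% |
| 0.75 | 0.7 | 0.5125 | 0.51 | 0.5% | 0.2% |
| 0.5 | 0.3 | 0.950 | 0.91 | 4% | 2.1% |
| 0.5 | 0.5 | 0.750 | 0.75 | 0% | 0.0% |
| 0.5 | 0.7 | 0.550 | 0.51 | 8% | 3.7% |

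**Validity of the t-test.** In 10,000 simulated trials with no treatment effect (300 pairs per arm, rho = 0.5, equal SDs), the two-sample t-test on change rejected in 5.2% at a nominal 5%. The issue is precision, not type I error.

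**Windows, side by side.**

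- Protocol 9.1 and 9.2.2: preferred days 360 − 30 = 330 to 360 + 30 = 390; otherwise the last echo in days 180-360.
- Protocol 9.7: days 360 − 90 = 270 to 360 + 90 = 450; or the last echo in days 180-360.
- Days 391-450: inside the 9.7 window, but in neither the preferred window nor the fallback of 9.1 and 9.2.2.
- Days 270-329: in window under 9.7, but only a fallback under 9.1 and 9.2.2.

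A subject with several echoes could therefore contribute a different one depending on which section is followed.

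**The case against.** The strongest reply is that nothing depends on this analysis. The endpoint is exploratory, sits outside the testing hierarchy and has no stated power. The change-score t-test is unbiased under randomization, and a chance baseline imbalance is not a bias across randomizations; it is the same precision point seen in a single trial. SAP 4.1 also has all variables summarised descriptively by treatment group, so the t-test is not the only view of the gradient. All of this stands, and it limits the weight of the point.

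A reader might infer that a change score loses precision whenever the correlation is below 1, and so that the 18-54% penalty applies here. The documents do not support that. The inference needs equal SDs, which neither document gives. The eligibility cap applies to the baseline echo and not to the later one, so a smaller baseline SD is plausible, though not shown. With r = rho = 0.5 the loss is zero.

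On timing, a reader might infer that Protocol 9.1 and 9.2.2 exclude a day-420 echo outright. Their wording is softer: the 30-day tolerance is a preference and the fallback is permissive, so 9.7 could be read as an outer collection range. Such an echo is ambiguous rather than barred. Even so, no section says which echo to analyse, and the SAP does not settle it.

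**Conclusion.** The point holds as a modest improvement. The planned test is valid, and adjusting for the screening gradient is at least as precise in large samples and usually more so. The cost of not adjusting is roughly 0-54% more echo pairs: 18-54% with equal SDs, and about 0-22% with a baseline SD of half to three quarters of the follow-up SD. These figures rest on assumed correlations of 0.3 to 0.7 and on a two-sample test. Outside that range the loss can be larger; for example, r = 1 and rho = 0.1 give 1.8/0.99, or 82% more pairs.

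The adjusted model also reports a difference in the protocol's own variable, the level at about 360 days. It would be wrong to conclude that the SAP's use of change targets a different treatment effect: with randomized arms the expected difference in change equals the expected difference in level. Nor does adjustment cure selection through death or missing echoes, since either analysis as described needs both measurements.

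The window mismatch is real but minor, and its effect on the result cannot be quantified from the documents.

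**What to change.** In SAP 6.5, replace the t-test with a linear regression of the day-360 gradient on treatment and screening gradient. Report the adjusted difference between strategies, its 95% CI and the number of echo pairs per arm. A valve-in-valve covariate is optional and not needed for this purpose.

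In the same section, state one analysis window in days and a rule for choosing among several echoes, saying how echoes on days 270-329 and 391-450 are handled. Placing this in the SAP is enough for the analysis. Aligning the text of Protocol 9.1, 9.2.2 and 9.7 would be tidier, but it means amending the protocol and can wait for another reason to do so.

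The cost is one model statement and a few lines of SAP text. No new data are needed, and the primary and secondary analyses are unchanged.
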